9.8. Tolerability Variables and Analysis

Since this is a single-dose study, tolerability is not specifically defined.

9.9. Biomarker Analysis

Biomarker results will be summarized using descriptive statistics. Analyses correlating efficacy variables and biomarkers will be explored as appropriate.

9.10. Immunogenicity Analysis

ADA information will be described for subjects who test positive. Samples from placebo-treated patients will not be analyzed.

9.11. Planned Interim Analysis

There will be no formal interim analysis.

9.12. Reporting Deviations from the Statistical Plan

Deviations from the statistical plan, along with the reasons for the deviations, will be described in protocol amendments, the statistical analysis plan, the CSR, or any combination of these, as appropriate, and in accordance with applicable national, local, and regional requirements and regulations.

10. DIRECT ACCESS TO SOURCE DATA AND DOCUMENTS

The medical experts, study monitors, auditors, IEC/IRB, and inspectors from competent authority (or their agents) will be given direct access to source data and documents (eg, medical charts/records, laboratory test results, printouts, videotapes) for source data verification, provided that patient confidentiality is maintained in accordance with national and local requirements.

The investigator must maintain the original records (ie, source documents) of each patient's data at all times. Examples of source documents are hospital records, office visit records; examining physician's finding or notes, consultant's written opinion or notes, laboratory reports, drug inventory, study drug label records, diary data, protocol-required worksheets, and CRFs that are used as the source (see Section 3.13).

The investigator will maintain a confidential patient identification list that allows the unambiguous identification of each patient. All study-related documents must be kept until notification by the sponsor.

11. QUALITY CONTROL AND QUALITY ASSURANCE

11.1. Protocol Amendments and Protocol Deviations and Violations

11.1.1. Protocol Amendments

No changes from the final approved (signed) protocol will be initiated without the prior written approval or favorable opinion of a written amendment by the IEC/IRB and national and local competent authorities, as applicable, except when necessary to address immediate safety concerns to the patients or when the change involves only nonsubstantial logistics or administration. The principal investigator at each investigational center, the coordinating investigator (if applicable), and the sponsor will sign the protocol amendment.

11.1.2. Protocol Violations

Any deviation from the protocol that affects, to a significant degree, (a) the safety, physical, or mental integrity of the subjects of the study and/or (b) the scientific value of the study will be considered a protocol violation. Protocol violations may include non-adherence on the part of the patient, the investigator, or the sponsor to protocol-specific inclusion and exclusion criteria, primary objective variable criteria, or GCP guidelines; noncompliance to study drug administration; use of prohibited medications. Protocol violations will be identified and recorded by investigational center personnel in the CRF. All protocol violations will be reported to the responsible IEC/IRB, as required.

When a protocol violation is reported, the sponsor will determine whether to discontinue the patient from the study or permit the patient to continue in the study, with documented approval from the medical expert. The decision will be based on ensuring the safety of the patient and preserving the integrity of the study.

Changes in the inclusion and exclusion criteria of the protocol are **not** prospectively granted by the sponsor. If investigational center personnel learn that a patient who did not meet protocol inclusion and exclusion criteria was entered in a study, they must immediately inform the sponsor of the protocol violation. If such patient has already completed the study or has withdrawn early, no action will be taken but the violation will be recorded.

11.2. Information to Study Personnel

The investigator is responsible for giving information about the study to all personnel members involved in the study or in any element of patient management, both before starting the study and during the course of the study (eg, when new personnel become involved). The investigator must ensure that all study personnel are qualified by education, experience, and training to perform their specific task. These study personnel members must be listed on the investigational center authorization form, which includes a clear description of each personnel member's responsibilities. This list must be updated throughout the study, as necessary.

The study monitor is responsible for explaining the protocol to all study personnel, including the investigator, and for ensuring they comply with the protocol. Additional information will be

made available during the study when new personnel members become involved in the study and as otherwise agreed upon with either the investigator or the study monitor.

11.3. Study Monitoring

To ensure compliance with GCP guidelines, the study monitor or representative is responsible for ensuring that patients have signed the informed consent form and the study is conducted according to applicable SOPs, the protocol, and other written instructions and regulatory guidelines.

The study monitor is the primary association between the sponsor and the investigator. The main responsibilities of the study monitor are to visit the investigator before, during, and after the study to ensure adherence to the protocol, that all data are correctly and completely recorded and reported, and that informed consent is obtained and recorded for all patients before they participate in the study and when changes to the consent form are warranted, in accordance with IEC/IRB approvals.

The study monitor will contact the investigator and visit the investigational center at regular intervals throughout the study. The study monitor will be permitted to check and verify the various records (CRFs and other pertinent source data records, including specific electronic source document [see Section 3.13]) relating to the study to verify adherence to the protocol and to ensure the completeness, consistency, and accuracy of the data being recorded. If electronic CRFs are used for the study, the study monitor will indicate verification by electronically applying source document verification flags to the CRF and will ensure that all required electronic signatures are being implemented accordingly.

As part of the supervision of study progress, other sponsor personnel may, on request, accompany the study monitor on visits to the investigational center. The investigator and assisting personnel must agree to cooperate with the study monitor to resolve any problems, errors, or possible misunderstandings concerning the findings detected in the course of these monitoring visits or provided in follow-up written communication.

11.4. Clinical Product Complaints

A clinical product complaint is defined as a problem or potential problem with the physical, chemical, micro-biological quality, or characteristics of clinical drug supplies or clinical device supplies used in a clinical research study sponsored by Teva. Examples of a product quality-related complaint include but are not limited to:

- suspected contamination
- questionable stability (eg, color change, flaking, crumbling, etc)
- defective components
- missing or extra units (eg, primary container is received at the investigational center with more or less than the designated number of units inside)
- incorrect packaging, or incorrect or missing labeling/labels
- unexpected or unanticipated taste or odor, or both

- device not working correctly or appears defective in some manner

Each investigational center will be responsible for reporting a possible clinical product quality related complaint by completing the product quality complaint form provided by Teva and emailing it to [REDACTED] within 2 business days of becoming aware of the issue.

For complaints involving a device or other retrievable item, it is required that the device (or item) be sent back to Teva for investigative evaluation whenever possible. For complaints involving a drug product, all relevant samples (eg, the remainder of the patient's drug supply) should be sent back to Teva for investigative evaluation whenever possible.

11.4.1. Product Quality Related Complaint Information Needed from the Investigational Center

In the event that the product quality complaint form cannot be completed, the investigator will obtain the following information, as available:

- investigational center number and principal investigator name
- name, phone number, and address of the source of the complaint
- clinical protocol number
- patient identifier (patient study number) and corresponding visit numbers, if applicable
- product name, lot number, and strength for open-label studies
- patient number, bottle, and kit numbers (if applicable) for double-blind or open-label studies
- product available for return Yes/No
- product was taken or used according to protocol Yes/No
- description or nature of complaint
- associated adverse event Yes/No
- clinical supplies unblinded (for blinded studies) Yes/No
- date and name (clinical study site) of person receiving the complaint

Note: Reporting a product quality related complaint must not be delayed even if not all the required information can be obtained immediately. Known information must be reported immediately. The sponsor will collaborate with the investigator to subsequently obtain any outstanding information.

11.4.2. Handling of Study Drug at the Investigational Center

The investigator is responsible for retaining the product in question in a location separate from the investigator's clinical study supplies. The sponsor may request that the investigator return the product for further evaluation and/or analysis. If this is necessary, the clinical study monitor or designee will provide the information needed for returning the study drug.

If it is determined that the investigational center must return all study drug, the sponsor will provide the information needed to handle the return.

The integrity of the randomization code and corresponding blinded clinical supplies will be maintained whenever possible. A serious adverse event or the potential for a product quality problem existing beyond the scope of the complaint may be a reason to unblind the clinical supplies for an affected patient.

11.4.3. Adverse Events or Serious Adverse Events Associated with a Product Complaint

If there is an adverse event or serious adverse event due to product complaint, the protocol should be followed for recording and reporting (Section 7.1.2 and Section 7.1.5.3, respectively).

11.4.4. Documenting a Product Complaint

The investigator will record in the source documentation a description of the product complaint, and any actions taken to resolve the complaint and to preserve the safety of the patient. Once the complaint has been investigated by the sponsor and the investigator, if necessary, an event closure letter may be sent to the investigational center where the complaint originated or to all investigational centers using the product.

11.5. Audit and Inspection

The sponsor may audit the investigational center to evaluate study conduct and compliance with protocols, SOPs, GCP guidelines, and applicable regulatory requirements. The sponsor's Global Clinical Quality Assurance, independent of Global Clinical Development, is responsible for determining the need for (and timing of) an investigational center audit.

The investigator must accept that competent authorities and sponsor representatives may conduct inspections and audits to verify compliance with GCP guidelines.

12. ETHICS

Details of compliance with regulatory requirements and applicable laws are provided in Section 1.6.

12.1. Informed Consent

The investigator, or a qualified person designated by the investigator, should fully inform the patient of all pertinent aspects of the study, including the written information approved by the IEC/IRB. All written and oral information about the study will be provided in a language as nontechnical as practical to be understood by the patient. The patient should be given ample time and opportunity to inquire about details of the study and to decide whether or not to participate in the study. The above should be detailed in the source documents.

Written informed consent will be obtained from each patient before any study-specific procedures or assessments are done and after the aims, methods, anticipated benefits, and potential hazards are explained, according to the IEC/IRB requirements. The patient's willingness to participate in the study will be documented in the informed consent form, which will be signed and personally dated by the patient and by the person who conducted the informed consent discussion. The investigator will keep the original informed consent forms, and copies will be given to the patients. It will also be explained to the patients that the patient is free to refuse participation in the study and free to withdraw from the study at any time without prejudice to future treatment.

Patients will provide written informed consent prior to completing the PET/CT scans.

12.2. Competent Authorities and Independent Ethics Committees/Institutional Review Boards

Before this study starts, the protocol will be submitted to each IEC/IRB for review. As required, the study will not start before the IEC/IRB for the investigational center gives written approval or a favorable opinion.

12.3. Confidentiality Regarding Study Patients

The investigator must ensure that the privacy of the patients, including their identity and all personal medical information, will be maintained at all times. In CRFs and other documents or image material submitted to the sponsor, patients will be identified not by their names, but by an identification number.

Personal medical information may be reviewed for the purpose of patient safety or for verifying data in the source and transcribed to the CRF. This review may be conducted by the study monitor, properly authorized persons on behalf of the sponsor, Global Quality Assurance, or competent authorities. Personal medical information will always be treated as confidential.

12.4. Declaration of the End of Clinical Study

The last visit (visit 7) is defined as end of treatment (approximately week 6). This will be considered the end of the trial for the purposes of end of trial notification

12.5. Registration of the Clinical Study

In compliance with national and local regulations and in accordance with Teva standard procedures, this clinical study may be registered on clinical trials registry websites.

13. DATA HANDLING, DATA QUALITY CONTROL, AND RECORD KEEPING

13.1. Data Collection

Data will be collected using CRFs that are specifically designed for this study. The data collected on the CRFs will be captured in a clinical data management system (CDMS) that meets the technical requirements described in 21CFR Part 11. The CDMS will be fully validated to ensure that it meets the scientific, regulatory, and logistical requirements of the study before it is used to capture data from this study. Before using the CDMS, all users will receive training on the system and study-specific training. After they are trained, users will be provided with individual system access rights.

Data will be collected at the investigational center by appropriately designated and trained personnel, and CRFs must be completed for each patient who provided informed consent. Patient identity should not be discernible from the data provided on the CRF. Data will be verified by the study monitor using the data source, and reviewed for consistency by Data Management using both automated logical checks and manual review. All data collected will be approved by the investigator at the investigational center. This approval acknowledges the investigator's review and acceptance of the data as being complete and accurate.

If data are processed from other sources (eg, central laboratory, bioanalytical laboratory, central image center, electronic diary data, electronic patient-reported outcome Tablet), the results will be sent to the investigational center, where they will be retained but not entered in the CRF, unless otherwise specified in the protocol. These data may also be sent electronically to the sponsor (or organization performing data management) for direct entry in the clinical database. Laboratory test results will not be entered in the CRF unless otherwise specified in the protocol. All data from other sources will be available to the investigators.

For patients who enter a study but do not meet entry criteria, at a minimum, data for screening failure reason, demography, and adverse events from the time of informed consent will be entered in the CRF.

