3.7. Randomization and Blinding

This is a randomized, double-blind, placebo-controlled study. After the 2 baseline PET/CT scans and successful completion of all requirements (Part 1), patients will be randomly assigned 1:1 in a double-blind fashion to receive either placebo or iv 3.0 mg/kg reslizumab.

In order to maintain the blind, each patient will be assigned a unique identifier number and all reference to the patient will be by using this identifier.

Patients will be randomly assigned to treatment groups by means of a computer-generated randomization list. The specifications for randomization will be under the responsibility and

oversight of Teva Global Statistics. The output of the randomization process will be a patient randomization list.

The sponsor's clinical personnel involved in the study will be blinded to the study drug identity until the database is locked for analysis and the treatment assignment is revealed, with the exception of the bioanalytical group who will not be blinded to facilitate ADA sample analysis and an un-blinded person who will be responsible for randomization assignment. Additionally, in order to maintain the study blind, blood and sputum eosinophil levels assessed after study drug administration will not be available to investigators, their blinded staff, the sponsor, and blinded members of the clinical research organization. There will be un-blinded data management, un-blinded site staff, and an un-blinded CRA who will not sit on the study team and be responsible for un-blinded eosinophil data.

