3.13. Source Data Recorded on the Case Report Form

All patient data must have supportive original source documentation in the medical records, or equivalent, before they are transcribed to the CRF. Data may not be recorded directly on the CRF and considered as source data unless the sponsor provides written instructions specifying which data are permitted to be recorded directly to the CRF.

If data are processed from other institutions or means (eg, clinical laboratory, central image center, or electronic diary data) the results will be sent to the investigational center, where they will be retained and transcribed to the CRF. All data from other institutions will be available to the investigator.

The CRFs are filed in the sponsor's central file.

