3.14.3.2. Weeks 2, 4, and 6 (Visits 5, 6, and 7)

The following procedures/assessments will be performed at weeks 2, 4, and 6 (visits 5, 6, and 7):

The following procedures will be performed at the CRTC of the [REDACTED]:

- Perform urine pregnancy test (for women of child bearing potential)
- Perform urine glucose test
- Perform PET/CT scan
- Observe for 1 hour after completion of PET/CT scan

Up to 72 hours after the PET/CT scan, the following procedures will be performed:

- Inquire about adverse events
- Inquire about concomitant medication usage
- Perform clinical laboratory tests (chemistry [week 6, visit 7 only], urinalysis [week 6, visit 7 only], and hematology). The results of the differential blood tests performed after study drug administration will be blinded. If there is a medical need to review these results, the investigator will contact the medical monitor.
- Collect sputum sample. The results of the sputum eosinophil assessments performed after study drug administration will be blinded. If there is a medical need to review these results, the investigator will contact the medical monitor.
- Perform physical examination:
 - brief exam at week 2 (visit 5) and week 4 (visit 6)

- complete exam at week 6 (visit 7) only
- Assess vital signs, including BP, pulse, RR, body temperature, and SpO₂
- Administer the AQLQ+12
- Obtain blood sample for serum ADA assay (weeks 2 and 6 [visits 5 and 7] only)
- Obtain blood sample for biomarkers analyses
- Perform spirometry

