6.1.3. Calculations

The radiology center will determine the following:

GLG is the total FDG uptake in the whole lung.

An ROI is drawn around lung boundary in each axial slice. SUVmean and area of each ROI is recorded. Using the formula: area*slice thickness the volume of each slice is calculated. Then SUVmean of each slice is multiplied by the volume of the corresponding slice, which will represent the total FDG uptake in one slice. This number for each slice is summed together to provide GLG of that lung.

$$GLG = \sum_1^n (area * slice\ thickness * SUVmean)$$

n=number of slices

Intra-patient variability (reproducibility measure):

Below is the calculation to determine the intra-patient variability between PET/CT scans as measured by GLG for HCs and patients with eosinophilic asthma. The accepted variability within each group is $\leq 10\%$ and will be as follows:

Relative difference of GLG=(GLG2-GLG1)/GLG1

Relative difference of GLG=(GLG4-GLG3)/GLG3

1= First time point (HCs)

2= Second time point (HCs)

3= First time point (patients with eosinophilic asthma)

4= Second time point (patients with eosinophilic asthma)

Variability between HC group and individual patients with eosinophilic asthma:

The planned method to assess whether the difference in GLG (Δ GLG) between HC subjects, as a group, and individual patients with eosinophilic asthma is $\geq 5\%$ and will be as follows:

For Females:

Relative difference of GLG=(GLG6_i-GLG5f)/GLG5f

For Males:

Relative difference of GLG=(GLG6_i-GLG5m)/GLG5m

5=average of 1 and 2

6=average of 3 and 4

GLG6_i will be calculated for each individual patient using his/her two measurements, and if that amount is $\geq 5\%$, than the patient will be randomized.

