### 1.1.2 Secondary Objectives and endpoints

The secondary objectives of the study are to demonstrate a correlation between the benefit observed on imaging (PET/CT) with:

- reductions in blood eosinophil counts
- improvement in clinic visit lung function
- reductions in fractional exhaled nitric oxide (FeNO)
- improvements in Asthma Quality of Life questionnaire (AQLQ) scores.

The secondary efficacy endpoints are:

- the change from baseline to week 4 in blood eosinophil counts
- the change from baseline to week 4 in FEV1
- the change from baseline to week 4 in FeNO
- the change from baseline to week 4 in AQLQ.

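### The protocol's data-access rules do not withhold post-dose GLG and SUVmean from the site, so scan results may be known before later AQLQ and spirometry that are correlated with GLG

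*Protocol*

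**What the plan says.** Protocol 13.1 lists its outside sources as "central laboratory, bioanalytical laboratory, central image center, electronic diary data, electronic patient-reported outcome Tablet". Their results go to the investigational center and may also go electronically to the sponsor or the data-management organization. It then states: "All data from other sources will be available to the investigators". Protocol 3.13, which also names a central image center, has the parallel sentence: "All data from other institutions will be available to the investigator". Neither sentence has an exception or a date. Protocol 13.1 also requires the investigator to approve all collected data.

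The exception for post-dose results is in Protocol 3.7: "blood and sputum eosinophil levels assessed after study drug administration will not be available to investigators, their blinded staff, the sponsor". SAP 2.2 repeats it, and Protocol 3.14.3.2 and footnotes f and g of the schedule tables in both documents apply it. No imaging variable appears in any of these places.

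Protocol 6.1.3 assigns the GLG calculation: "The radiology center will determine the following". On timing, Protocol 3.14.3.2 lists the scan first for weeks 2, 4 and 6 and continues: "Up to 72 hours after the PET/CT scan, the following procedures will be performed". AQLQ and spirometry are among those procedures. Protocol 3.1 and SAP 2.1 describe the opposite order, with the clinic visit first and the scan within 3 days after it.

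SAP 1.1.2 states the use of the data: "The secondary objectives of the study are to demonstrate a correlation between the benefit observed on imaging (PET/CT) with" blood eosinophils, clinic lung function, FeNO and AQLQ. SAP 6.3 does this with Spearman's rho on the week-4 changes.

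**The concern.** A correlation between change in GLG and change in FEV1 or AQLQ is informative only if each is measured without knowledge of the other. If someone who runs or discusses the week-4 tests has seen how the scan moved, effort, coaching or reporting can follow the scan. A correlation could then arise from scan noise alone, in the placebo arm as well, and without anyone knowing the treatment. The treatment blind does not guard against this.

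The plan already holds back post-dose eosinophils to protect the blind. GLG is the primary endpoint, and the second primary objective expects reslizumab to lower it, yet it has no such protection. Aligning Protocol 3.13 and 13.1 with the present list in 3.7 would not close the gap, because GLG is not on that list.

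**Working it through.** **Step 1: which results are open to the site.** The general rule (Protocol 3.13, 13.1) opens all outside data to the investigators. The exception (Protocol 3.7, SAP 2.2) removes post-dose blood and sputum eosinophils. What remains open includes GLG, SUVmean, and lymph node and bone marrow uptake at visits 5, 6 and 7.

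**Step 2: which scans come before the week-4 tests.**

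| Visit order | Week-2 scan before week-4 AQLQ/FEV1 | Week-4 scan before week-4 AQLQ/FEV1 |
|---|---|---|
| Protocol 3.14.3.2 (scan, then clinic) | yes | yes |
| Protocol 3.1, SAP 2.1 (clinic, then scan) | yes | no |

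This is the order of the scans, not of the results. The documents give no turnaround for post-dose reading. Fast reading is assumed feasible at one point: visit 3 GLG decides eligibility, and visit 4 falls within 72 hours of that scan (Protocol 3.14.3.1, Table 2).

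**Step 3: which correlates are exposed.** FEV1 depends on effort. AQLQ is self-reported. FeNO is a measured gas value, and blood eosinophils are laboratory counts already withheld; both are little exposed.

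**Step 4: scale, for illustration only.** The plan has no figure to reproduce. Let g be the standardized week-4 improvement in GLG and e independent noise with SD 1. With no true link, take the secondary change as y = e + b·g, where b is the assumed influence in SD units. Spearman's rho was simulated with n = 10 (both arms together, no missing data) and 40,000 replicates:

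| b | Mean rho | Chance that rho ≥ 0.5 | 95% range of rho |
|---|---|---|---|
| 0 | 0.00 | 7% | −0.64 to 0.64 |
| 0.25 | 0.21 | 20% | −0.47 to 0.77 |
| 0.5 | 0.40 | 41% | −0.25 to 0.85 |
| 1 | 0.64 | 78% | 0.10 to 0.93 |

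The sign refers to improvement. With ΔGLG as defined in SAP 6.2.1, a fall is negative and the sign reverses for endpoints where higher is better.

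**Step 5: only week-2 GLG known.** On the Pearson scale the induced correlation is b/√(1+b²) when week-4 GLG is known: 0.24, 0.45 and 0.71 for b = 0.25, 0.5 and 1. If only week-2 GLG is known, it is multiplied by the correlation between the week-2 and week-4 GLG changes. If that is 0.5 (an assumption), the values halve to 0.12, 0.22 and 0.35.

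**The case against.** The access sentences read as general text. Protocol 13.1 is conditional and lists a diary and a tablet that appear in no procedure of this study. It names a central image center, whereas the study's reader is called the radiology center. Being available could mean after the last visit, and manual ROIs on every slice give no reason to expect a quick post-dose result. This tempers the likelihood. It does not remove the gap, because no provision delays or withholds these results.

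A reader might infer more than the documents support:

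- *That patients learn their GLG.* Protocol 1.4.2.2 provides only for communicating incidental findings.
- *That the staff who receive GLG also run the tests.* The access sentences name the investigators; no section says who administers AQLQ or spirometry.
- *That staff can readily move the values.* AQLQ is self-administered (SAP 6.3.4.1), so any influence is indirect. Spirometry follows ATS/ERS 2005 (Protocol 6.2), which limits the coaching effect.
- *That GLG unblinds treatment.* A fall in blood eosinophils is a known drug effect (Protocol 1.3.2.2). Protocol Table 1 says whole-lung inflammation under anti-IL-5 therapy versus placebo has not been reported, so the site has no established pattern to read. At most GLG is a weak clue.
- *That the primary endpoint is biased.* Site staff seeing earlier GLG does not change how later GLG is measured.

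The correlations are also descriptive, in a study called exploratory. With no influence at all, rho from 10 patients already ranges from −0.64 to 0.64. That limits the stakes, but it also means the final data could not separate a modest influence from chance.

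**Conclusion.** The gap in the text is real: a stated access rule covers image-center data, and the list of exceptions omits post-dose GLG and SUVmean. What follows is a possible loss of independence in two of the four secondary correlations, those with FEV1 and AQLQ. Bias is not demonstrated.

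Its size cannot be derived from the documents. The mean rho values of 0.21, 0.40 and 0.64 rest on an assumed b, no true link, 10 patients analyzed together and week-4 GLG known before the week-4 tests. The last condition is open only under the Protocol 3.14.3.2 order; under Protocol 3.1 and SAP 2.1 the effect is smaller. A b of 1 would be an extreme influence. The point merits a change because prevention is cheap and no analysis can remove the influence afterwards.

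**What to change.** - **Withheld list.** In Protocol 3.7 and SAP 2.2, add the visit 5 to 7 PET results: GLG, SUVmean, and lymph node and bone marrow uptake. Except them from the general access sentences in Protocol 3.13 and 13.1.
- **Data route.** The radiology center sends these results directly to the unblinded data management already provided for in Protocol 3.7, by the electronic transfer that 13.1 allows. They must be in the database before lock, so holding them at the radiology center until lock would not work. Blinded site staff and sponsor clinical staff do not see them while any patient still has AQLQ or spirometry to complete.
- **Approval.** Amend the investigator-approval sentence in 13.1 so that approval of these data takes place after the last patient's visit 7 and before lock, or is exempted.
- **Unchanged.** Visit 2 and 3 GLG is still released for inclusion criteria k and l, and incidental findings are still reported.
- **Reconcile.** Protocol 3.1 and SAP 2.1 must be reconciled with Protocol 3.14.3.2 on the order of scan and clinic visit.

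The cost is a few sentences, a transfer instruction and a small change to data flow, with no new procedures for patients. Site staff see post-dose GLG later.
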